### 5.4.1 Analysis of Efficacy Endpoints Based on Tumor Response

ORR, duration of response (DOR), time to response and PFS will be analyzed on the FAS for HCC subjects and Response Evaluable Set as appropriate.

The exact 95% confidence intervals of ORR will be calculated using Clopper-Pearson method. DOR and time to response will be for subjects who have achieved a best response of CR or PR only. Censoring rules for PFS will follow the FDA guidance and are specified in Table 5. PFS will be reported in both summary tables and plotted with Kaplan-Meier curve.

**Table 5 Censoring Rules for PFS**

No.	Situation	Date of Event (Progression/Death) or Censoring	Outcome
1	No baseline tumor assessments	Date of first dose	Censored
2	Progression documented between scheduled visits	Date of first radiologic PD assessment	Event
3	No progression	Date of last adequate radiologic assessment	Censored
4	New anticancer treatment started	Date of last adequate radiologic assessment prior to or on date of new anticancer treatment	Censored
5	Death before first PD assessment	Date of death	Event
6	Death between adequate assessment visits*	Date of death	Event
7	Death or progression after more than one missed visit/tumor assessment**	Date of last adequate radiologic assessment before missed tumor assessments	Censored

CR = complete response, PD = progressive disease, PR = partial response, SD =stable disease,

\* Adequate tumor assessment is radiologic assessment of CR, PR, SD, non-CR/non-PD or PD at regular interval as defined in the protocol.

\*\* More than one missed visit/adequate tumor assessment is defined as having either one of the following two durations being longer than 14 weeks - 1 day, which is 97 days ( $= ((6+1) \times 2 \times 7) - 1$ ) for subjects on the every 6 week tumor assessment schedule:

- Duration between two consecutive tumor assessments
- Duration between the last adequate tumor assessment and death or PD

The priority of the censoring rules is as follows,

- If the subject had PD or death, the following sequence will be applied:
  - If a subject did not have a baseline tumor assessment (No. 1), the subject will be censored on the date of first dose.
  - If the subject died within 97 days (14 weeks -1 day) following first dose and did not receive a new anticancer treatment, it will be counted as PFS event at the date of death.

- If a subject had new anticancer treatment before PD or death (No. 4), the subject will be censored on the date of the last adequate tumor assessment prior to or on the date of new anticancer treatment.
- If a subject missed two or more tumor assessments before PD or death (No. 7), the subject will be censored on the date of the last adequate tumor assessment before PD or death. Note that if a subject is censored by both this criterion and the anticancer treatment criterion, the earliest censoring date will be used.
- Otherwise, if a subject had an event (No. 2, No. 5, or No. 6), the earliest event date will be used.

2. If a subject did not have PD or death, the censoring date will be the earliest censoring date if the subject met multiple censoring criteria (No. 1, No. 3, No. 4, No. 7).

A listing of target lesion response, non-target lesion response, new lesion and overall response at each assessment time point will be provided. Best overall response will be identified in the listing.

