All subjects are required to undergo chest, abdomen, and pelvis imaging at baseline and all follow-up time points. Contrast-enhanced CT scan of the chest and contrast-enhanced CT scan or MRI of the abdomen, pelvis, and any other areas of disease, as clinically indicated, will be acquired at Screening and at all imaging time points. A liver CT scan or MRI must be performed using triphasic scanning techniques optimized to capture precontrast, arterial, and portal venous phases. Copies of all tumor imaging scans must be retained by the investigators. If requested by the Sponsor or by the health authorities, these copies will be sent to an imaging core laboratory designated by the Sponsor for quality assessment, archiving, and potential future review. Historical standard-of-care scans conducted within 28 days prior to study drug administration may be used as screening/baseline imaging if scanning parameters are consistent with the requirements for this protocol as separately defined by the imaging core laboratory.

MRI scans (optimized for precontrast, arterial phase, and portal venous phase) may be used instead of CT scans for imaging of the abdomen and pelvis. However, the chest must be imaged using CT; and chest disease must be followed by CT scan (ie, chest x-ray for response assessment is not allowed). If iodinated intravenous (IV) contrast is contraindicated, chest CT scan should be performed without IV contrast.

Imaging studies are to be repeated during the Treatment Phase and Extension Phase every 6 weeks, or more frequently if clinically indicated, until disease progression, withdrawal of

consent, or the subject receives another anticancer therapy. The same method of assessment used during Screening must be used at all subsequent time points.

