#### 5.1.2 Secondary Endpoints

- PK: standard primary PK parameters including, but not limited to, the area under the plasma concentration-time curve from 0 through last measurable point (AUC0-t), maximum observed plasma concentration (Cmax) and time of maximum observed plasma concentration (tmax).
- Preliminary antitumor activity: Response will be determined by the investigator using mRECIST/RECIST 1.1. The following endpoints will be determined:
  - Objective response rate (ORR), defined as the proportion of subjects achieving a best overall confirmed response of partial or complete response (partial response [PR] + complete response [CR]) from first dose date until disease progression/recurrence.
  - Duration of response (DOR), defined as the time from the date of first documented CR/PR until the first documentation of disease progression as determined by the investigator or death, whichever comes first. If a subject had no record of disease progression or did not die before the data cut-off date, then the subject will be censored at the last available tumor assessment.
  - Progression free survival (PFS), defined as the time from first dose date to the date of the first documentation of disease progression as determined by the investigator or death, whichever occurs first.

- Overall survival (OS), defined as the time from first dose date to the date of death.
- Time to response, defined as the time from first dose date to the date of first documented CR/PR.

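### The PFS missed-scan rule does not exclude the pre-dose baseline scan, so one missed Week 6 scan can cause a Week 12 progression to be censored, with no usable censoring date

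*SAP*

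**What the plan says.** SAP 5.1.2 starts PFS at first dose: it is "defined as the time from first dose date to the date of the first documentation of disease progression" or death. SAP 5.4.1 analyses it on the Full Analysis Set for HCC subjects, which under SAP 5.2.1 means every dosed HCC subject.

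Table 5 row 7 censors a progression or death that follows more than one missed assessment. The double-asterisk footnote sets the threshold, "which is 97 days", and applies the rule if either of two gaps is longer than that:

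- "Duration between two consecutive tumor assessments"
- "Duration between the last adequate tumor assessment and death or PD"

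Rows 3, 4 and 7 all place the censoring date at the last adequate assessment. The single-asterisk footnote defines the term: "Adequate tumor assessment is radiologic assessment of CR, PR, SD, non-CR/non-PD or PD at regular interval as defined in the protocol".

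The priority list under the table uses first dose as its anchor in two places. The first is a missing baseline scan: "If a subject did not have a baseline tumor assessment (No. 1), the subject will be censored on the date of first dose". The second is early death: "If the subject died within 97 days (14 weeks -1 day) following first dose", with no new anticancer treatment, the death is an event.

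On scan timing, Protocol 9.5.1.2.1 says: "Historical standard-of-care scans conducted within 28 days prior to study drug administration may be used as screening/baseline imaging". The same section repeats imaging every 6 weeks and equates C3 Day 1 with 6 weeks after first dose. The footnotes to Protocol Tables 6 and 7 put the first response scan at Week 6.

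**The concern.** The first gap carries neither the word adequate nor any limit to post-baseline scans, while row 1 and the priority list call the pre-dose scan a tumor assessment. Taken as written, the interval from baseline to the first on-study scan is therefore a gap between consecutive assessments. It includes up to 28 days before treatment, which the 97-day allowance was not built to absorb. One missed scan can then be classed as more than one, and a documented progression stops counting as an event.

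The outcome would depend on how long before dosing the baseline scan was taken, which says nothing about follow-up on treatment. It would also treat progression and death differently after the same missed scan, because only the death step counts from first dose.

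The date is a second problem. A subject with a baseline scan but no adequate post-baseline scan has no last adequate assessment to be censored at. SAP 5.3.5 foresees subjects who leave before any response assessment, but it gives a rule for them only in the response rate.

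**Working it through.** **The plan's figure.** ((6 + 1) × 2 × 7) − 1 = 98 − 1 = 97 days. This reproduces. The footnote says longer than 97, so a gap of 98 days or more triggers the rule.

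**Inputs.** Baseline scan b days before first dose, b = 1 to 28 (Protocol 9.5.1.2.1). On-study scans due 42, 84 and 126 days after first dose (Weeks 6, 12 and 18).

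**Week 6 done on time.** The gap from baseline is 42 + b, at most 42 + 28 = 70 days. The rule is never triggered.

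**Week 6 missed, progression on an on-time Week 12 scan.** The gap is 84 + b.

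| Baseline lead b (days) | Gap (days) | Over 97? |
|---|---|---|
| 1 | 85 | no |
| 13 | 97 | no |
| 14 | 98 | yes |
| 20 | 104 | yes |
| 28 | 112 | yes |

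One missed scan is classed as more than one when b is 14 or more. If durations are counted as date difference plus 1, the cut-off is 13.

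**Sensitivity to the Week 12 scan date.** The smallest b that triggers the rule is 98 minus the scan day counted from first dose:

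- 7 days early: 98 − 77 = 21, so 8 of the 28 permitted baseline days trigger the rule
- 3 days early: 98 − 81 = 17, so 12 of 28
- on time: 98 − 84 = 14, so 15 of 28
- 3 days late: 98 − 87 = 11, so 18 of 28
- 7 days late: 98 − 91 = 7, so 22 of 28

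If baseline scans were spread evenly over the window, which is an assumption and not in the documents, 15/28 = 54% of subjects with this pattern would be flagged (8/28 = 29% to 22/28 = 79%).

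**The same single miss later on.** Week 6 done, Week 12 missed, progression at Week 18: 126 − 42 = 84 days, an event.

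**Death instead of progression.** A death 84 days after first dose without new therapy is within 97 days of first dose. The priority list makes it an event, whatever the baseline lead.

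**Censoring date.** The flagged progression is to be censored at the last adequate assessment before the gap. The only earlier scan is the baseline scan. It has no response category and is not one of the regular on-study scans, so the single-asterisk footnote excludes it. No date remains. The same holds under rows 3 and 4 for a subject with a baseline scan and no adequate post-baseline scan who is alive without progression or has started new therapy. Row 1 does not help, because it covers only a missing baseline scan.

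**The case against.** The text can be read as an on-study clock. The double-asterisk footnote defines missed visits or adequate assessments on the 6-week schedule, and 97 days is built from two such intervals with a week's allowance each. The second gap says adequate, and the priority list speaks of two or more missed assessments, which a single missed Week 6 scan is not. That is probably what was meant. It does not settle the matter, because either gap alone triggers the rule and the first gap is not so limited. The first-dose anchor that would protect the subject is written for death only. For a subject with no adequate post-baseline scan, the second gap has no starting point either.

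SAP sections 8 and 9 leave further conventions to separate programming specifications, which may supply a default date. That could fill the gap in rows 3 and 4, where most analysts would choose first dose anyway. Whether a progression counts as an event belongs in the SAP.

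Two stronger readings are tempting, and the documents support neither.

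- A reader might infer that PFS times fall before first dose. Under the single-asterisk footnote the date is undefined. A time of −28 to −1 days arises only if a programmer treats the baseline scan as adequate.
- A reader might infer that PFS is overstated, because progressions are removed while subjects with the same missed scan and no progression stay in. But the last item of the priority list takes the earliest censoring date for subjects without progression or death, and it includes row 7. Under the same literal reading those subjects are flagged too. Row 7's own title mentions only death or progression, so the text leaves their handling unclear. If both groups are removed alike, the selective loss disappears. Any figure for the shift would also need a missed-scan rate and a PFS distribution, and the documents give neither.

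**Conclusion.** The concern holds in a limited form. It affects subjects who miss the Week 6 scan and progress at the next one, with a baseline scan 14 or more days before first dose (7 to 21 days for a Week 12 scan 7 days late to 7 days early). For them, the literal rule turns a valid progression into a censored observation without a usable date, while a death on the same day without new therapy would count. Subjects scanned on time at Week 6 are unaffected. The missing date in rows 3 and 4 is real, but on its own it would be a minor gap.

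The calendar arithmetic needs no outside assumption. The 54% figure does, and how many subjects would be affected is unknown. The direction and size of any bias in PFS are not established. PFS is a descriptive secondary endpoint here, so no sample size or error rate depends on the rule. The correction is still worth making before database lock, because it decides which progressions count.

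**What to change.** In the double-asterisk footnote to SAP Table 5, restrict the first gap to post-baseline assessments. Add that, when there is no earlier adequate post-baseline assessment, the 97 days run from first dose for progression as well as for death. In rows 3, 4 and 7, add that a subject with no adequate post-baseline assessment before the censoring point is censored at the date of first dose.

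With these changes, Week 6 missed and progression at Week 12 gives 84 days (91 if the scan is 7 days late), which is an event. Weeks 6 and 12 both missed and progression at Week 18 gives 126 days, which is censored at time zero. This matches how the rule already behaves later in follow-up.

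The cost is two or three sentences in the SAP, a matching line in the programming specifications and a small programming change. No new data are needed.

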MRI scans may be used instead of CT scans for imaging of the abdomen and pelvis. However, the chest must be imaged using CT; and chest disease must be followed by CT scan (ie, chest x-ray for response assessment is not allowed). The same method of assessment used during Screening must be used at all subsequent time points. If iodinated intravenous contrast is contraindicated, chest CT scan should be performed without intravenous contrast.

A brain scan should be performed for all subjects to assess potential central nervous system disease and/or metastases as clinically indicated. For eligible subjects with previously treated brain metastases, a brain scan will be required at all tumor assessment time points (eg, every 6 weeks). For all subjects, a follow-up brain scan must be performed to confirm a complete response (CR) within 1 week following response confirmation.

The first radiological assessment of tumor response status will be performed during Week 6, unless there is clinical indication warranting earlier radiologic imaging. Response assessments will be repeated every 6 weeks until disease progression as determined by the investigator. Although clinical progression may be determined by the investigator based upon clinical deterioration, every effort should be made to document progression using radiographic methods. Signs and symptoms of clinical deterioration that lead to disease progression should be documented.

Subjects discontinued from treatment without disease progression will continue to undergo tumor assessments every 6 weeks until documented disease progression or initiation of another anticancer therapy.

Subjects who discontinue study treatment, regardless of their reasons for doing so, will be followed for survival approximately every 12 weeks for up to 12 months or until 6 cycles after last patient in, death, loss to follow-up, or withdrawal of consent, whichever occurs first.

Pharmacokinetic Assessments

Plasma samples for PK analyses will be collected during C1 on Day 1, Day 8, and Day 15 in Part 1, Dose Escalation. Plasma samples for PK analyses will be collected during C1 on Day 8, and Day 15 in Part 2, Expansion, according to the Schedule of Assessments.

Urine and plasma samples for assessment of the metabolite profile will be collected during C1 on Day 8 for urine and Day 1, Day 8, and Day 15 for plasma in Part 1, Dose Escalation, only.

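### When scans resume after a gap of more than 97 days, SAP PFS rule 7 gives two censoring dates and censors events that directly follow an adequate scan

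*SAP*

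**What the plan says.** SAP Section 5.4.1 applies a missed-assessment rule to PFS, No. 7 in Table 5. Four pieces of text define it.

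- **Table 5, row 7.** The situation is "Death or progression after more than one missed visit/tumor assessment" and the censoring date is the "Date of last adequate radiologic assessment before missed tumor assessments".
- **Double-asterisk footnote.** The rule is triggered when either of two durations is "longer than 14 weeks - 1 day, which is 97 days": (a) "Duration between two consecutive tumor assessments" or (b) "Duration between the last adequate tumor assessment and death or PD". Nothing says where in follow-up the gap in (a) must lie.
- **Priority list, item 1 (subjects with PD or death).** For a subject who meets No. 7, "the subject will be censored on the date of the last adequate tumor assessment before PD or death". Counting the event (Nos. 2, 5 or 6) comes last and applies only if the censoring items above it did not. The one earlier item that counts an event is death within 97 days of first dose without new anticancer treatment.
- **Priority list, item 2 (subjects without PD or death).** "If a subject did not have PD or death, the censoring date will be the earliest censoring date" where several criteria are met, and No. 7 is named beside Nos. 1, 3 and 4.

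The scan schedule is in the Protocol synopsis: "Response assessments will be repeated every 6 weeks until disease progression as determined by the investigator". Protocol Section 9.7.1.6 right-censors subjects without progression or death at their last response evaluation.

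**The concern.** Row 7 and the priority list cite the same rule number but fix the date by different landmarks: one by the missed scans, the other by the event. A subject whose scans resume after a long gap therefore has two censoring dates, and the SAP does not say which one governs.

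Separately, trigger (a) reaches gaps that ended long before the event. A progression or death seen soon after an adequate scan can then be censored because of an unrelated earlier gap.

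Lastly, item 2 applies No. 7 to subjects with no event, although row 7 requires one.

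At stake are the Kaplan-Meier PFS estimate, reported by dose schedule in Part 2 with 40 subjects planned per schedule, and whether two programmers working from this SAP would produce the same curve.

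**Working it through.** **Inputs.** Scan interval 6 weeks = 42 days (Protocol synopsis). Threshold 97 days (SAP Table 5 footnote). The scan histories below are illustrations, because the documents hold no patient data.

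**Step 1: reproduce the threshold.** ((6 + 1) × 2 × 7) − 1 = 98 − 1 = 97 days, the same as 14 × 7 − 1. The SAP figure is exact.

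**Step 2: what the threshold catches.** One scan missed on schedule leaves 2 × 42 = 84 days, which is not flagged. Two consecutive misses leave 3 × 42 = 126 days, which is flagged.

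**Step 3: apply the text literally.** In every history there is stable disease at weeks 6 and 12 (days 42 and 84), and weeks 18 and 24 are missed.

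| History after the gap | Last interval before event | Row 7 date | Priority-list date |
|---|---|---|---|
| A: PD at week 30 (day 210) | 210 − 84 = 126 days | day 84 | day 84 |
| B: SD at week 30, PD at week 36 (day 252) | 252 − 210 = 42 days | day 84 (week 12) | day 210 (week 30) |
| C: SD at weeks 30 and 36, death on day 280 | 280 − 252 = 28 days | day 84 | day 252 |

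- In A the gap runs into the event and the two dates coincide.
- In B they differ by 210 − 84 = 126 days, and in C by 252 − 84 = 168 days.
- In B and C the event is not counted under either date. Trigger (a) is met by the gap from day 84 to day 210, so the final event item is never reached. The early-death item does not help, because both events fall well after day 97.
- Follow-up after the gap is lost only under the row 7 date. The priority-list date keeps the scans up to the last one before the event.

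**Step 4: is trigger (a) needed?** Trigger (b) already covers every gap that ends in PD or death. For a subject with an event, trigger (a) therefore adds only earlier gaps, as in B and C.

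**Step 5: event-free subjects.** History D has SD at weeks 30 and 36 and no event. No. 3 gives day 252. If No. 7 is applied with the row 7 date, it gives day 84, and the earliest-date instruction selects day 84. That drops 252 − 84 = 168 days (24 weeks) of observed progression-free time and contradicts Protocol Section 9.7.1.6, which gives day 252. The priority-list date cannot be computed for D, because there is no PD or death to count back from.

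**Step 6: apply rule 7 only when the interval ending in PD or death exceeds 97 days.** A stays censored at day 84. B becomes an event at day 252 and C an event at day 280. D is censored at day 252.

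**The case against.** The best defence is that the problem is narrow. In the ordinary case, where scans stop and PD or death follows, the two texts agree. They part only when scans resume, without PD, after at least two consecutive misses. Counting baseline as the scan before the gap, misses at weeks 6 and 12, a stable scan at week 18 and PD at week 24 is the shortest such pattern on the 6-week grid. Protocol Section 9.1.2.4 anticipates about 4 months on treatment, and Section 9.5.1.2.1 says interruptions in therapy should not shift the scan schedule. The pattern may well be uncommon. It remains possible, since treatment can run longer and subjects who stop without PD go on being scanned every 6 weeks.

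The SAP also places further conventions and derivation rules in separate programming specifications (Sections 8 and 9), which may fix one date. That would settle the programming but not the contradiction in the SAP, which is where the rule is stated.

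The SAP ties its censoring to FDA guidance, which cannot be consulted here. These documents alone therefore cannot settle whether an earlier long gap ought to censor a later event. That part of the fix is a choice of convention. The argument for it is that in history B the PD is located to within one scheduled interval.

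A reader might also infer three stronger things that the text does not support:

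- **That rule 7 acts on gaps that do not precede the event.** In subjects with an event, the gap does precede it, though not necessarily immediately.
- **That both dates discard follow-up.** The priority-list date keeps follow-up to the last scan before the event.
- **That event-free subjects certainly lose 24 weeks.** Row 7 requires death or progression, so an event-free subject arguably never meets No. 7, and its mention in item 2 then has no effect. The loss follows only if No. 7 is applied despite that definition.

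**Conclusion.** The inconsistency is real, and it is confined to subjects whose scans resume after a gap over 97 days. For them the SAP gives two censoring dates (week 12 against week 30 in history B), and under either one a PD or death that directly follows an adequate scan is not counted. The listing of No. 7 for event-free subjects is at least unclear and, if applied, departs from the Protocol.

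The documents give no rate of missed scans, so the number of subjects affected cannot be estimated. With 40 subjects in a schedule, each one is 1/40 = 2.5% of that group. PFS is a secondary, descriptive endpoint. The consequence is for the Kaplan-Meier PFS estimate and its reproducibility, not for any hypothesis test or the sample size, whose Part 2 precision table concerns ORR. The correction should be made, but it does not threaten the trial's primary conclusions.

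**What to change.** Make three edits to SAP Section 5.4.1:

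1. State one rule 7 date in both Table 5 and the priority list: the last adequate assessment before the gap.
2. Apply rule 7 only when the interval from the last adequate assessment preceding PD or death to that event exceeds 97 days, and delete the gap between consecutive assessments as a trigger in its own right. With this restriction the two dates coincide.
3. Remove No. 7 from item 2, so that No. 3 censors event-free subjects at their last adequate scan, in line with Protocol Section 9.7.1.6.

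If the sponsor does want an earlier gap to censor a later event, the SAP should say so explicitly and still give a single date.

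The cost is a wording change and a small programming change, with no new data. It is best done before PFS results are seen, so that the choice cannot look data-driven.
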